#### 2.5 Randomization

This is a randomized trial and subjects are randomized into Sham Control Arm or Latera Implant Treatment Arm, after anesthetic is delivered. Treatment assignment will remain blinded to the study subject through the 3-month assessment.

The graphic below illustrates the flow of subjects in the study and potential points of study exit relative to the analysis plan (**Figure 1**, below). Subjects are enrolled at the time of consent, and the ITT population is comprised of all consented subjects. Subjects are randomized after the anesthetic is administered. Subjects in the active treatment group receive the Latera implant, while those in the Sham Control group will undergo insertion of the cannula into the nasal lateral wall, but the Latera will not be implanted. The mITT population includes all subjects who were randomized, irrespective of whether they received the study device. The PP population includes those subjects who received the study device or the Sham Control and who are followed through 3 months.

<sup>1 Kittelson JM, Emerson SS. A unifying family of group sequential test designs. Biometrics. 1999 Sep;55(3):874-82.

ST 800-A

# STATISTICAL ANALYSIS PLAN

Figure 1. Flow of subjects in the trial and definitions of the ITT, mITT and PP populations.

# STATISTICAL ANALYSIS PLAN

#### 2.6 Study Activities and Assessments

 Table 1. Schedule of Study Activities

Х		Visit	Visit 4 - 30	Visit 5 - 90 ± 14 days*	Cross-Over Screening (for Sham Control Subjects	Cross-Over Procedure (for Sham Control Subjects	Visit 6 –	Visit 7 – 12 months	Visit 8 – 18	Visit 9 – 24 months
					Х					
Х										
Х										
Х				Х			Х			
X										
Х			Х	Х	Х		Х	Х	Х	Х
Х			Х	Х	Х		Х	Х	Х	Х
Х										
Х										
Х		Х	Х	Х	X		Х	Х	Х	Х
	Х									
	Х					Х				
Х		Х	Х	Х			Х	Х	Х	Х
Х	Х	Х	Х	Х		Х	Х	Х	Х	Х
	X X X X X X X X X X X X	X X X X X X X X X X X X X X X X X X X	X X X X X X X X X X X X X X X X X X X	X     X       X     X	XXX	XXXX $X$ XX $X$ XX $X$ XX $X$ XX $X$ $X$ X $X$ $X$	XXX<	XXXXX $X$ XXX $X$ XXX $X$ XXX $X$ XXX $X$ XXX $X$ $X$ XX $X$ $X$ $X$ X $X$	X       X       X       X         X       X       X       X       X         X       X       X       X       X       X         X       X       X       X       X       X       X         X       X       X       X       X       X       X         X       X       X       X       X       X       X         X       X       X       X       X       X       X         X       X       X       X       X       X       X         X       X       X       X       X       X       X         X       X       X       X       X       X       X         X       X       X       X       X       X       X         X       X       X       X       X       X       X         X       X       X       X       X       X       X         X       X       X       X       X       X       X       X         X       X       X       X       X       X       X       X         X	X       X       X       X       X       X       X         X       X       X       X       X       X       X       X         X       X       X       X       X       X       X       X         X       X       X       X       X       X       X       X         X       X       X       X       X       X       X       X         X       X       X       X       X       X       X       X         X       X       X       X       X       X       X       X         X       X       X       X       X       X       X       X         X       X       X       X       X       X       X       X         X       X       X       X       X       X       X       X         X       X       X       X       X       X       X       X       X         X       X       X       X       X       X       X       X       X       X         X       X       X       X       X       X       X       X<

# STATISTICAL ANALYSIS PLAN

The schedule of study activities (Table 1, above) specifies the assessments that will be completed at each follow up visit. Below are the descriptions of the Patient Reported Outcomes (PRO)\_ assessments and Lateral Wall Motion Video assessment:

#### Nasal Obstruction Symptom Evaluation (NOSE) scale

The Nasal Obstruction Symptom Evaluation (NOSE) scale is a PRO instrument that will be administered to capture subject perception of the degree of nasal airway patency.

The NOSE scale is a validated instrument, developed by the American Academy of Otolaryngology—Head and Neck Surgery (AAO-HNS), and has been used in several clinical trials. The scale is brief, easy to complete, and is an important tool for pre- and post-intervention evaluation of symptoms in subjects with nasal obstruction.

Subjects will be asked: "Since your last follow up visit, how much of a problem were the following conditions for you?" Specifically, subjects will be asked to rate their perceptions on the Likert scale with respect to the following characteristics:

- Nasal congestion or stuffiness
- Nasal blockage or obstruction
- Trouble breathing through my nose
- Trouble sleeping
- Unable to get enough air through my nose during exercise or exertion

Subjects will rate their responses using a Likert scale with response options 0, 1, 2, 3 or 4, as follows:

- Not a Problem
- Very Mild Problem
- Moderate problem
- Fairly Bad Problem
- Severe problem

The responses are rated along the continuum, with a rating of "0 – not a problem" indicating no problem breathing, with a completely free flow of air through the nasal airway; "1 – very mild problem", with only slight obstruction in airflow; "2 – moderate problem", with mouth breathing

## STATISTICAL ANALYSIS PLAN

considered easier; "3 - fairly bad problem," with considerable obstruction to airflow; and a rating of "4 - severe problem," with complete blockage and obstruction of the nasal passageway, where the subject cannot breathe through the nose and can only mouth breathe.

#### Nasal Breathing Assessment

A subject's perception of breathing cannot be quantitatively measured but exists on a continuum from the subject perspective. The VAS is a PRO instrument that will be used to capture subjects' perception of their ability to breathe through the nose, allowing subjects to indicate the degree of breathing difficulty (or ease) they are currently experiencing.

Operationally, the VAS is a horizontal line, 100mm in length, anchored by word descriptors at each end, as illustrated in **Figure 2**. The subject will mark on the line the point that they feel represents their perception of their current state and the electronic PRO form will automatically calculate the score for VAS. The VAS score is determined by measuring in millimeters from the left end of the line to the point marked by the subject.

No difficulty/ Easy to Breathe Through the Nose		Unable to Breathe Through the Nose 🛞
---	--	--

Figure 2: Visual Analog Scale. Left side represents 0 mm and right side represents 100 mm.

#### Epworth Sleepiness Scale (ESS)

The Epworth Sleepiness Scale (ESS) is a widely-used PRO in the field of sleep medicine as a subjective measure of a patient's sleepiness.

ST 800-A

## STATISTICAL ANALYSIS PLAN

The test is a list of eight situations that evaluate a subject's tendency to become sleepy on a scale of 0 (no chance of dozing), to 3 (high chance of dozing). The scale estimates whether the subject is experiencing excessive sleepiness that may possibly require medical attention.

Subjects will be asked: "How sleepy are you? How likely are you to doze off or fall asleep in the following situations?" They will be asked to rate their chances of dozing off, not just feeling tired and even if they have not done some of these things recently to try and determine how they would have affected them. For each situation, subjects will be asked to decide if they would have:

•	No chance of dozing	0
•	Slight chance of dozing	1
•	Moderate change of dozing	2
•	High chance of dozing	3

Using the above scale, subjects will write down the corresponding choice to the following situations:

- Sitting and reading
- Watching TV
- Sitting inactive in a public place (e.g. a theater or a meeting)
- As a passenger in a car for an hour without a break
- Lying down to rest in the afternoon when circumstances permit
- Sitting and talking to someone
- Sitting quietly after lunch without alcohol
- In a car, while stopped for a few minutes in traffic

The responses to the above situations is totaled for a final composite score.

#### Pittsburg Sleep Quality Index

The Pittsburgh Sleep Quality Index (PSQI) is a questionnaire used to assess sleep quality over the previous 1-month. The measure consists of 19 individual items, creating 7 components that produce one total score. Component scores consist of subjective sleep quality, sleep latency (i.e., how long it takes to fall asleep), sleep duration, habitual sleep efficiency (i.e., the percentage of

## STATISTICAL ANALYSIS PLAN

time in bed that one is asleep), sleep disturbances, use of sleeping medication, and daytime dysfunction.

#### Lateral Wall Motion Video Assessment

Video results from Endoscopy assessments will be captured and transferred to Spirox. The videos will be de-identified prior to transfer to an independent reviewer. The independent reviewer will make assessment of endoscopic lateral wall insufficiency score (1, 2 or 3).

#### 2.7 Retrievals and Re-Implantation

There is a low incidence of where the Latera Implant is removed, post-implant nasal manipulation by a patient. If this occurs, the Latera Implant may be re-implanted, within 30 days, of the removal at the discretion of the investigator, continuing the follow up schedule from the Index Procedure. An addendum to the Informed Consent is required to be reviewed and signed by subject. See Section 4.1.1 for analysis implications.

#### **3 ENDPOINT DEFINITIONS**

#### 3.1 Primary Endpoint

The primary endpoint of the study is the Responder Rate, assessed 3 months post-procedure in the per protocol population of the Latera and Sham arms. Responder Rate is defined as the proportion of subjects with at least one (1) NOSE class improvement or at least 20% NOSE score reduction.

#### 3.2 Secondary Endpoints

The following endpoints comprise the secondary endpoints and the time points that each will be assessed:

• Responder Rate at 7 days, 30 days, and 6, 12, 18 and 24 months;

## STATISTICAL ANALYSIS PLAN

- Frequency of procedure-related adverse events (non-serious and serious), assessed at the index procedure and through the 7-day, 30-day, 3-month, 6-month, 12-month, 18-month, and 24-month follow-up time points;
- Frequency of device-related adverse events (non-serious and serious), assessed at the index procedure and through the 7-day, 30-day, 3-month, 6-month, 12-month, 18-month and 24-month follow-up time points;
- NOSE score, change from baseline, to the 7-day, 30-day, 3-month, 6-month, 12-month, 18-month, and 24-month follow-up time points;
- Visual Analogue Scale (VAS), change from baseline, to the 7-day, 30-day, 3-month, 6-month, 12-month, 18-month, and 24-month follow-up time points;
- Endoscopic lateral wall insufficiency (LWI) score as assessed by independent reviewers, change from baseline to the 3-month and 6-month time points;
- Epworth Sleepiness Scale (ESS) score and Pittsburg Sleepiness Quality Index, change from baseline, to the 7-day, 30-day, 3-month, 6-month, 12-month, 18-month, and 24-month follow-up time points.

All secondary endpoints will be assessed for the Sham Control Arm at two additional visits. The Sham arm will have follow-up visits at 7 days, 30 days, and 3 months after the initial treatment/randomization, and 30 days, 3 months, 6, months, 12 months, 18 months, and 24 months in subjects that cross over.

#### 4 ANALYSIS POPULATIONS

#### 4.1.1 Study Population

Adult male and female patients presenting with symptomatic nasal valve collapse due to or primarily due to insufficient cartilaginous support of the lateral nasal wall will be enrolled, if they meet all eligibility criteria. The study will include up to 150 subjects enrolled at up to 15 investigational sites in the US. The maximum enrollment per site will be 20% of the total enrollment number therefore a 30-subject maximum per site. Initial site enrollment will be limited to 20-subjects and written permission from Sponsor will be required to enroll up to 30 subjects maximum.

ST 800-A

### STATISTICAL ANALYSIS PLAN

The following populations will be analyzed in the study:

**Intention-to-Treat (ITT) Population:** The ITT analysis will be performed on all enrolled subjects in the study, irrespective of adherence with the entry criteria, treatment actually received, subsequent withdrawal, or deviation from the Clinical Investigational Plan. Subjects who are enrolled but not randomized will not be included in the analytic datasets.

Modified Intention-to-Treat (mITT) Population: The mITT Population will comprise of ITT subjects who received anesthetic, regardless of whether they received the Latera Implant or underwent the Sham procedure. Subjects who are in the mITT population assigned to the Latera Implant Arm but who do not receive the device are followed for 3 months for safety-related endpoints and will be exited after 3-month follow-up assessments.

**Per Protocol Population:** The PP analysis will be performed on randomized subjects a) in the Sham Control Arm, and b) in the Latera Implant Arm who were treated and who had NOSE score assessments within the 3-month follow-up clinic visit window. The primary endpoint will be evaluated on this population. Subjects will be analyzed according to the procedure actually received in the event of mis-randomization. Unblinded subjects in either arm prior to the 3-month time point are not included in the PP analysis.

The point of enrollment into the study occurs when the subject signs the Informed Consent Form (ICF) and meets all eligibility criteria.

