4.4. Withdrawals and Loss to Follow-up

Participation is completely voluntary and each subject is free to withdraw from the study at any time. An investigator also has the right to withdraw the subject from the study in the event of reasons concerning the health or well-being of the subject, or in the case of lack of cooperation. Should a subject decide to withdraw for any reason, or should the investigator decide to withdraw the subject, all efforts will be made to complete and report the observations up to the time of withdrawal as thoroughly as possible. A complete final evaluation at the time of the subject's withdrawal must be made and an explanation given of why the subject is withdrawing or being withdrawn from the study.

The reason for and date of withdrawal must be recorded on the subject's Study Exit Case Report Form (CRF). If the reason for the withdrawal is a device-related or procedure related AE, the event must be reported to the Sponsor and recorded in the AE CRF.

Withdrawal can occur at several time-points that would impact the follow up schedule for a study subject. If withdrawal occurs any time before the treatment procedure, anesthesia and randomization, the subject will be exited with no follow up assessment requirements. If withdrawal occurs after anesthesia,

regardless of whether randomization is complete, subjects will be followed through the 3 months follow up assessment and then exited from the study.

All efforts will be made to retain subjects in order to collect data at all the follow-up visits (7 days, 30 days, 3 months, 6 months, 12 months, 18 months, 24 months). Due diligence in reaching the subject must include:

- Two documented telephone contact attempts, emails, or regular postal mail letters, and
- A certified letter

After the above attempts are made, if no response is obtained, the Study Exit CRF page will need to be completed and communication attempts will need to be documented.

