 - iii. In addition, anesthesia may be injected along the proposed implantation track, starting at the alar rim and progressing to the supra-periosteal region of the maxilla. Additional injections into alar rim may also be considered.
 - d. Wait approximately 10 minutes for anesthesia to be in full effect.
- 6. RANDOMIZATION: Subjects are randomized into the Sham Control Arm or the Latera Implant Treatment Arm, after anesthetic is delivered. Treatment assignment will remain blinded to the study subject.
- In the event the subject is selected for the Latera Implant Arm, the implants (bilateral) will be delivered in a loaded delivery tool, using standard deployment technique per Spirox IFU (Attachment C). Only one Implant per side may be placed.
- 8. In the event the subject is selected for the Sham Control Arm, follow the exact same process for implant delivery per Spirox IFU (**Attachment C**), including pulling the alar rim back allowing insertion of the cannula of an unloaded (no implant) delivery tool. No implant is deployed in the Sham Control Arm.

The following data will be recorded on the subject's procedure CRF:

- Anesthesia regimen
- Photograph image with Trajectory Plan
- The Randomization Assignment
- All medication administered pre- and post-procedure.
- Implant placement or sham control logistical information
- Any adverse events or adverse device effects observed during this visit will be collected and documented.

Data collected for the Treatment Visit should be entered into the EDC no later than five (5) business days after the completion of procedure/visit.

IMPORTANT: Prior to discharge, provide the post-procedure reminder form and instructions for managing the post procedure recovery time. In addition, a course of antibiotics (e.g. Amoxicillin, Augmentin or equivalent) may be prescribed by the physician pursuant to local practice standards. Upon completion of the treatment visit, the subject will be scheduled for their next Follow-Up Visit.

Note: Space intentionally left blank.

Table 2. Schedule of Study Activities

Visits (± Windows)	Screening/Baseline	Index Procedure - Day 0	Visit $3 - 7 \pm 2$ days	Visit 4 - 30 ± 7 days*	Visit 5 - 90 ± 14 days*	Cross-Over Screening (for Sham Control Subjects only)	Cross-Over Procedure (for Sham Control Subjects only)	Visit $6 - 6$ month ± 14 days	Visit $7 - 12$ months ± 30 days	Visit $8 - 18$ months ± 30 days	Visit $9 - 24$ months ± 30 days
Informed Consent	Х					Х					

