8. RISK-BENEFIT ANALYSIS

8.1. Risks to the Subjects

The list below described the general types of potential risks to the study subjects.

Adverse Events
Infection
Inflammation
Pain or discomfort
Serous wound drainage
Hematoma
Ecchymosis
Extrusion
Retrieval
Foreign body reaction
Foreign body sensation
Device Fracture
Device Malposition or Migration
Device Palpable
Skin Irritation
Allergic reaction to device
Allergic reaction to medications from procedure or follow up
Allergic reaction to any study related medications
Hematoma*, general (such as cannula insertion, delivery of anesthetics, manipulation of nose during procedure, etc.)
Perceptible cosmetic changes
Respiratory / sinus infection or rhinorrhea
Continued or worsened breathing symptoms
Scarring
Firmness, swelling, redness
Decreased sense of smell

*Includes hematoma from cannula insertion, delivery of anesthetics, manipulation of nose during procedure)

There are other health risks and discomforts associated with the testing that the subjects will undergo before and after their procedure, including but not limited to pain and bruising at the implant pierce point site or areas of anesthetic injections.

For subjects in the Sham Control Group, the use of anesthetic and insertion of the cannula imparts the same risks except for those directly attributable to an implant, without the potential benefit of the treatment.

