#### 5.3 Secondary Endpoint Analyses

The following endpoints comprise the secondary endpoints and the time points that each will be assessed:

- Responder Rate at 7 days, 30 days, and 6, 12, 18 and 24 months;
- Frequency of procedure-related adverse events (non-serious and serious), assessed at the index procedure and through the 7-day, 30-day, 3-month, 6-month, 12-month, 18-month, and 24-month follow-up time points;
- Frequency of device-related adverse events (non-serious and serious), assessed at the index procedure and through the 7-day, 30-day, 3-month, 6-month, 12-month, 18-month and 24-month follow-up time points;
- NOSE score, change from baseline, to the 7-day, 30-day, 3-month, 6-month, 12-month, 18-month, and 24-month follow-up time points;
- Visual Analogue Scale (VAS), change from baseline, to the 7-day, 30-day, 3-month, 6-month, 12-month, 18-month, and 24-month follow-up time points;
- Endoscopic lateral wall insufficiency (LWI) score as assessed by independent reviewers, change from baseline to the 3-month and 6-month time points;
- Epworth Sleepiness Scale (ESS) score and Pittsburg Sleepiness Quality Index, change from baseline, to the 7-day, 30-day, 3-month, 6-month, 12-month, 18-month, and 24-month follow-up time points.

All secondary endpoints will be assessed for the Sham Control Arm at two additional visits. The Sham arm will have follow-up visits at 7 days, 30 days, and 3 months after the initial

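### The rule that drops unrandomised subjects has no safety exception, so an anaesthetic event that stops the procedure before randomisation can fall out of the tabulated procedure-related AE rate

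*SAP*

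**What the plan says.** **Order of events.** SAP 2.5 states: "Subjects are randomized after the anesthetic is administered". Protocol 5.2 places a pause between the two steps: "Wait approximately 10 minutes for anesthesia to be in full effect". A subject can therefore be anaesthetised and never randomised.

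**Follow-up of such subjects.** Protocol 4.4 foresees this. For withdrawal after anaesthesia it says: "regardless of whether randomization is complete, subjects will be followed through the 3 months follow up assessment and then exited from the study".

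**Exclusion.** The ITT paragraph of SAP 4.1.1, with the same wording in Protocol 6.2, says: "Subjects who are enrolled but not randomized will not be included in the analytic datasets". The sentence is not limited to efficacy.

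**mITT, first definition** (SAP 4.1.1, Protocol 6.2): "The mITT Population will comprise of ITT subjects who received anesthetic, regardless of whether they received the Latera Implant or underwent the Sham procedure".

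**mITT, second definition** (SAP 2.5, Protocol 4.3): "The mITT population includes all subjects who were randomized, irrespective of whether they received the study device".

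**ITT.** SAP 2.5 and Protocol 4.3 take in everyone who consented. SAP 4.1.1 and Protocol 6.2 start from all enrolled subjects but leave the unrandomised out of the analytic datasets.

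**Endpoint.** SAP 5.3 lists as a secondary endpoint: "Frequency of procedure-related adverse events (non-serious and serious), assessed at the index procedure", and then through the follow-up visits. No analysis population is named for it. Neither document defines a safety population.

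**Relevant events.** Protocol 8.1 lists, among the potential risks, "Hematoma*, general (such as cannula insertion, delivery of anesthetics, manipulation of nose during procedure, etc", and separately lists allergic reactions to procedure medications.

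**The concern.** An event caused by the anaesthetic can be both a procedure-related adverse event and the reason the subject is not randomised. For such a subject, the event that the safety endpoint should count is what triggers the exclusion. The subject leaves the numerator and the denominator together, although the protocol has arranged 3 months of follow-up.

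At stake is whether the reported frequency of procedure-related events is complete. Anaesthesia is part of the procedure in both arms, so its harms belong in that frequency whether or not the subject goes on to receive an implant or a sham insertion.

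**Working it through.** The plan gives no figure on this point, so the check is mainly a comparison of definitions, followed by simple arithmetic on an assumed range.

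**1. Where does an anaesthetised, unrandomised subject fall?**

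| ITT wording used | mITT wording used | In ITT? | In mITT? |
|---|---|---|---|
| SAP 4.1.1 / Protocol 6.2 (unrandomised left out) | SAP 4.1.1 / Protocol 6.2 (ITT subjects given anaesthetic) | No | No |
| SAP 4.1.1 / Protocol 6.2 | SAP 2.5 / Protocol 4.3 (randomised) | No | No |
| SAP 2.5 / Protocol 4.3 (all consented) | SAP 2.5 / Protocol 4.3 | Yes | No |
| SAP 2.5 / Protocol 4.3 | SAP 4.1.1 / Protocol 6.2 | Yes | Yes |

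The per protocol set is limited to randomised subjects, so the answer there is always no.

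In the first row, mITT is built from ITT subjects. Everyone randomised has already had the anaesthetic. Once the unrandomised are removed, ITT and mITT therefore contain the same people, and the anaesthetic criterion adds nobody.

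**2. Does any planned table bring the subject back?**

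- SAP 5.3 compares binary secondary endpoints between treatment groups. An unrandomised subject has no group.
- SAP 5.4.1 summarises safety data by treatment but expressly leaves out AEs and SAEs.
- SAP 5.1 promises descriptive summaries of all data but names no population and does not lift the exclusion.
- SAP 4.2 refers to a per protocol dataset for secondary endpoints, which holds randomised subjects only.

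No planned table clearly counts these events.

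**3. Direction.** Let *a* of *n* randomised subjects have a procedure-related event, and let *k* further subjects have one that stops the procedure before randomisation. The randomised-only rate is *a/n* and the complete rate is *(a + k)/(n + k)*. Because *a ≤ n*, the first cannot exceed the second. This holds for stops caused by an event. Subjects who stop for another reason without an event would add to the denominator only.

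**4. Size.** Input: maximum enrolment of 150 (SAP 4.1.1). Assumption: all 150 receive anaesthetic. The number of stops is also assumed.

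| Stops caused by an event (assumed) | Share of 150 | Exact 95% CI |
|---|---|---|
| 1 | 1/150 = 0.7% | 0.02% to 3.7% |
| 2 | 2/150 = 1.3% | 0.2% to 4.7% |
| 3 | 3/150 = 2.0% | 0.4% to 5.7% |
| 5 | 5/150 = 3.3% | 1.1% to 7.6% |

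A randomised-only dataset shows none of these events.

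**5. Would the case arise at all?** With an assumed stop rate *r* (any reason, after anaesthesia and before randomisation), the expected number is 150*r* and the chance of at least one is 1 − (1 − *r*)^150:

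| *r* (assumed) | Expected | Chance of at least one |
|---|---|---|
| 0.5% | 0.75 | 53% |
| 1% | 1.5 | 78% |
| 2% | 3 | 95% |
| 5% | 7.5 | above 99.9% |

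**The case against.** The strongest reply has four parts.

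- **The text is contradictory, not uniformly exclusive.** The all-consented ITT of SAP 2.5, combined with the anaesthetic-based mITT of SAP 4.1.1, would hold exactly these subjects, and no population is named for the adverse event endpoint. This stands. A reader might infer that these subjects are removed from every dataset and that their events never count. The documents do not support that: it is the result of the explicit exclusion rule, but other wording points the other way.
- **The events are not lost.** Protocol 5.2 records events at the treatment visit, 9.2 requires every procedure-related event on the AE form, 9.3 has the Medical Monitor evaluate them all, and 9.4 has the DMC review safety in aggregate. This also stands. Only the tabulated endpoint is at risk.
- **The window is narrow.** Protocol 8.1 lists the risks but does not say that they stop a procedure. An event in a subject who is still randomised counts in the ordinary way. A reaction that stops the procedure after randomisation leaves the subject in ITT and mITT, and SAP 4.1.1 follows such Latera-arm subjects for safety. This limits the size but does not close the gap.
- **Unrandomised subjects cannot enter a between-arm test.** True, and nothing here asks for that. A descriptive frequency needs no arm.

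The denominator of 150 also deserves caution. It is maximum enrolment, and enrolment comes before anaesthesia. Subjects may leave before anaesthesia (Protocol 4.4) or because they are not treated within 30 days of consent (Protocol 5.1). With fewer anaesthetised subjects, each stop weighs slightly more: at 124, for example, 1/124 = 0.8%.

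**Conclusion.** The point holds as a gap between a stated exclusion rule and a stated safety endpoint, made worse by two unreconciled definitions each of ITT and mITT and by the lack of a safety population. Under the explicit rule, an anaesthetic-related event that stops the procedure before randomisation is left out of the tabulated procedure-related frequency, and omitting it can only understate that frequency.

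The size is probably small and cannot be fixed from the documents, which give no rate of such stops. On the assumption of 150 anaesthetised subjects, each one is worth about 0.7 percentage points. It would be wrong to infer that the safety rate is substantially biased, since that would require a count of stops and a background event rate that the plan does not supply. The primary endpoint and the Latera versus sham comparison do not change.

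**What to change.** 1. Limit the exclusion sentence in SAP 4.1.1 and Protocol 6.2 to the efficacy datasets.
2. Define a safety population of all subjects who received anaesthetic.
3. Name that population for procedure-related adverse events, and show unrandomised subjects in a separate column.
4. Keep all between-arm comparisons on randomised subjects.
5. Use one definition each of ITT and mITT in Protocol 4.3 and 6.2 and in SAP 2.5 and 4.1.1.

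The cost is wording in both documents and one more table column. No new data are needed, because the follow-up is already required. The stated adverse event rate may come out slightly higher.
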